4.1. Inclusion Criteria

1. Provision of signed and dated informed consent form (ICF)
2. Stated willingness to comply with all study procedures and availability for the duration of the study
3. Healthy adult male or female

4. Current nondependent, polydrug recreational user who has used opioid drugs for recreational (nontherapeutic) purposes (i.e., for psychoactive effects) at least 10 times in the subject's lifetime and at least once in the last 12 weeks from Screening; and has a history of recreational use of at least 2 or more of any of the perception-altering (e.g., lysergic acid diethylamide [LSD], kratom, cannabis, dronabinol, ketamine, phencyclidine [PCP], dextromethorphan, 3,4 methylenedioxymethamphetamine [MDMA], mescaline, psilocybin, tryptamine derivatives or ring-substituted amphetamines with perception altering effects) or stimulant (e.g., cocaine, amphetamine, methamphetamine, methylphenidate, methcathinone, and other synthetic cathinones) drugs on at least 5 occasions in the subject's lifetime
5. If male, meets one of the following criteria:
 - a) Is able to procreate and agrees to use one of the accepted contraceptive regimens and not to donate sperm from study drug administration to at least 90 days after study drug administration. An acceptable method of contraception includes one of the following:
 - Abstinence from heterosexual intercourse
 - Double-barrier method (e.g., male condom with spermicide or male condom with a vaginal spermicide [gel, foam, or suppository])
 - Or
 - b) Is unable to procreate; defined as surgically sterile (i.e., has undergone a vasectomy at least 180 days prior to study drug administration)
6. If female, meets one of the following criteria:
 - a) Is of childbearing potential and agrees to use an acceptable contraceptive method. Acceptable contraceptive methods include:
 - Abstinence from heterosexual intercourse from the Screening visit through to at least 30 days after study drug administration
 - or
 - One of the following contraceptive methods, used from at least 28 days prior to the Screening visit through to at least 30 days after study drug administration:
 - Systemic contraceptives (combined birth control pills, injectable/implant/insertable hormonal birth control products, or transdermal patch)
 - Intrauterine device (with or without hormones)
 - Male partner vasectomized at least 6 months prior to the Screening visit
 - or
 - One of the following double-barrier contraceptive methods, used from the Screening visit through to at least 30 days study drug administration:

- Male condom plus spermicide
- Diaphragm plus spermicide
- Cervical cap plus spermicide

Or

- b) Is of non-childbearing potential, defined as surgically sterile (i.e., has undergone complete hysterectomy, bilateral oophorectomy, or tubal ligation), or is in a postmenopausal state (i.e., at least 1 year without menses without an alternative medical condition prior to the Screening visit and follicle stimulating hormone levels ≥ 40 mIU/mL at Screening)
- 7. Aged at least 18 years but not older than 59 years (inclusive) at Screening
- 8. Body mass index (BMI) within 18.0 kg/m² to 34.0 kg/m², inclusively at Screening
- 9. Minimum weight of 50.0 kg at Screening
- 10. Have no clinically significant diseases captured in the medical history or evidence of clinically significant findings on the physical examination (including vital signs, oxygen saturation [SpO₂], and respiratory rate) and/or ECG, as determined by an Investigator

4.2. Exclusion Criteria

1. Difficulty swallowing capsules
2. Female who is lactating
3. Female who is pregnant according to the pregnancy test at Screening or prior to study drug administration
4. Male with female partner who is pregnant, lactating, or planning to become pregnant during this study or within 90 days after study drug administration
5. History of significant hypersensitivity to kratom or any related products (including excipients of the formulations) as well as severe hypersensitivity reactions (like angioedema) to any drugs
6. Presence or history of significant gastrointestinal, liver or kidney disease, or surgery that may affect drug bioavailability with the exception of cholecystectomy that is permitted at the discretion of an Investigator
7. History of significant hepatic, renal, cardiovascular, pulmonary, hematologic, neurological, psychiatric, gastrointestinal, endocrine, immunologic, ophthalmologic, or dermatologic disease

8. Presence of any significant respiratory illness or presence or history of chronic respiratory disease (e.g., upper respiratory illness, sleep apnea, emphysema, asthma) at Screening (subjects with acute respiratory illness may be rescheduled upon resolution at the discretion of an Investigator)
9. History of substance or alcohol moderate to severe use disorder (excluding nicotine and caffeine) within the past 2 years, as defined by the Diagnostic and Statistical Manual of Mental Disorders, 5th Edition (DSM-5)
10. Is a heavy smoker (> 20 cigarettes per day) and/or is unable to abstain from smoking or unable to abstain from the use of prohibited nicotine-containing products for at least 1 hour before and 8 hours after study drug administration (including e-cigarettes, pipes, cigars, chewing tobacco, nicotine topical patches, nicotine gum, or nicotine lozenges)
11. Regularly consumes excessive amounts of caffeine or xanthines, defined as greater than 6 servings (1 serving is approximately equivalent to 120 mg of caffeine) of coffee, tea, cola, or other caffeinated beverages per day
12. History of suicidal behavior within 2 years of Screening, showing suicidal tendency as per the C-SSRS administered at Screening ([APPENDIX 7](#)), or is currently at risk of suicide in the opinion of an Investigator
13. Presence of clinically significant ECG abnormalities at the Screening visit, as defined by medical judgment. Note: QT corrected according to Fridericia's formula (QTcF) interval of > 450 msec in male subjects or > 470 msec in female subjects will be exclusionary. The ECG may be repeated once for confirmatory purposes if the initial value obtained exceeds the limits specified.
14. Estimated glomerular filtration rate (eGFR) \leq 60 mL/min as calculated by the CKD-EPI equation
15. Any clinically significant illness in the 28 days prior to study drug administration
16. Use of any prescription drugs (with the exception of hormonal contraceptives or hormone replacement therapy) in the 28 days prior to study drug administration, that in the opinion of an Investigator would put into question the status of the participant as healthy
17. Use of St. John's wort in the 28 days prior to study drug administration
18. Positive test result for alcohol and/or drugs of abuse at admission (prior to study drug administration). Subjects with positive results at admission may be rescheduled at the discretion of an Investigator. If tetrahydrocannabinol (THC) is positive at admission a cannabis intoxication evaluation will be done by an Investigator and subjects may be permitted to continue in the study at the discretion of an Investigator. Other positive test

results should be reviewed to determine if the subject may be rescheduled, in the opinion of the investigator.

19. Positive screening results to HIV Ag/Ab combo, hepatitis B surface antigen or hepatitis C virus tests
20. Any other clinically significant abnormalities in laboratory test results at Screening that would, in the opinion of an Investigator, increase the subject's risk of participation, jeopardize complete participation in the study, or compromise interpretation of study data
21. Inclusion in a previous group for this clinical study
22. Intake of kratom in the 14 days prior to study drug administration
23. Intake of an Investigational Product (IP) in the 28 days prior to study drug administration
24. Donation of plasma in the 7 days prior to study drug administration
25. Donation of 1 unit of blood to American Red Cross or equivalent organization or donation of over 500 mL of blood in the 56 days prior to study drug administration
26. Subject cannot eat dairy and/or is lactose intolerant
27. Is, in the opinion of an Investigator or designee, considered unsuitable or unlikely to comply with the study protocol for any reason

4.3. Withdrawal Criteria

4.3.1. Before First Treatment Administration

Before the first treatment administration, inclusion/exclusion criteria will govern the subjects to be dosed. Subjects withdrawn before first treatment administration will not be followed up and will not undergo End-of-Study/Early Termination assessments. Other safety assessments may be performed if required.

Subjects are free to withdraw their consent to participate in the study at any time, without prejudice. The reason for their withdrawal or for deciding to end their participation will be documented.

4.3.2. After First Treatment Administration

Subjects may, at any time, voluntarily withdraw from the study or be removed from the study at the discretion of an Investigator or Sponsor. An Investigator may withdraw a subject at any time if it is determined that continuing the study would result in a significant safety risk to the subject or if their behavior is deleterious to the study environment. If such withdrawal occurs, or if the subject fails to return for visits, an Investigator should determine the primary reason for a

subject's premature withdrawal from the study and record the reason in the subject's study documents.

An Investigator may remove a subject from the study on the recommendation of the PK facility and/or Sponsor due to an unanticipated event that could result in an inadequately characterized PK profile (e.g., a missed blood draw, an AE, meal deviation, concomitant medication intake, etc).

In the case of a clinically significant illness detected during the trial (including Coronavirus Disease 2019 [COVID-19] diagnosis), the Principal Investigator (or delegate) will, in concert with the Sponsor, determine the most appropriate course of action on an individual basis.

Evaluations will include but are not limited to:

- The safety of the subject and other study participants
- The possible effect the illness would have on the results gathered during the trial, and their ability to be appropriately analyzed or interpreted
- The possibility of suspending participation then re-initiating it after recovery
- The implication of any inclusion or exclusion criteria that would contradict possible actions
- The implication of any adherence to regulatory guidelines that may be affected by actions decided; for example group effect analysis
- The sample size calculation, current number of subjects, and possibility of replacement subjects

Evaluations and decision-making for subject removal will be documented in the study file, reported to the Sponsor, and discussed where appropriate in the Clinical Study Report.

Attempts should be made to have such subjects complete the End-of-Study/Early Termination assessments. End-of-Study/Early Termination assessments should be performed as soon as possible after the last study treatment administration.

For subjects lost to follow-up (i.e., those subjects whose status is unclear because they fail to appear for study visits without stating an intention to withdraw), an Investigator should show "due diligence" by documenting in the source documents steps taken to contact the subject, e.g., dates of telephone calls, registered letters, etc.

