1. INTRODUCTION

1.1. Study Rationale

The Food and Drug Administration (FDA) has previously warned consumers about the use of kratom (*Mitragyna speciosa*). Kratom has both affinity and activity at mu opioid receptors, receptor sites known to be associated with abuse. Although kratom use is prevalent, to date, clinical evaluations of abuse potential have not been performed. The Controlled Substance Staff (CSS) at FDA is proposing to initiate a pilot, single ascending dose (SAD) study of botanical kratom. Currently there are limited safety data and chemical, manufacturing, and control data to support clinical research with botanical kratom and isolated kratom alkaloids. The present study will provide data in these areas that will inform future clinical research with kratom.

The dose escalation will include 5 cohorts (8 subjects per cohort) of subjects randomized to receive either active drug (kratom) or placebo (6:2 active:placebo). Following each dosing, safety and pharmacodynamic (PD) data will be reviewed by a safety review board to determine if further dose escalation can safely commence.

A placebo control is used to establish the frequency and magnitude of changes in clinical endpoints that may occur in the absence of active treatment as well as to minimize subject and investigator bias. Blinded treatment, including the use of double-blind procedures, will be used to reduce potential bias during data collection and evaluation of clinical endpoints.

The FDA guidance “Bioavailability Studies Submitted in NDAs or INDs — General Considerations” recommends conducting studies under fed conditions if tolerability issues or serious adverse events (SAEs) are anticipated under fasted conditions. The current study will therefore administer the study drug following intake of a high-fat breakfast to avoid potential tolerability issues (i.e., vomiting).

Subjects will be healthy individuals, with previous non-therapeutic (recreational) polydrug use and opioid experience. Furthermore, subjects will be required to have experience with drugs that have psychoactive properties, particularly since supratherapeutic (high) doses of kratom will be evaluated in this study.

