7.4. Adverse Event Monitoring

For the purposes of this study, the monitoring period for AEs extends from the pre-trial evaluation until collection of the last blood sample of the study. From screening to dosing of the study, AEs will be recorded as screening events or as part of the medical history, as applicable.

AEs occurring after initiation of study drug will be indicated as TEAEs in the clinical study report.

Subjects will be questioned on their health status at the beginning of each study period and before each departure from the clinical site. Open-ended questions will be asked.

During the study, all AEs spontaneously reported by the subject, observed by the clinical staff or elicited by general questioning will be recorded for all subjects and reported in the CRF.

If necessary, every effort will be made to obtain an adequate follow-up of the subjects. Should any subject choose to withdraw from the study, they will be advised of the safety precautions to be taken.

Any AE which remains unresolved as of the last visit will require an evaluation and follow-up until the AE has been resolved or a reasonable explanation for its persistence found, or is deemed mild and safely resolving.

In the case of AEs deemed related to the Investigational Product, every effort will be made to determine the final outcome.

It is an Investigator's responsibility to ensure subjects experiencing AEs receive appropriate follow-up, treatment where required, and that every action is well documented.

Classification of AEs will be performed by System Organ Class (SOC) and Preferred Term (PT) using the Medical Dictionary for Regulatory Activities (MedDRA), version 24.0 or higher.

Concomitant medications will be coded using the World Health Organization drug dictionary (WHO-DDE March 2021 or later).

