### **4.3 Pharmacokinetic Population**

The PK population will include all subjects who have received at least 1 dose of the investigational product (IP) and have at least 1 mitragynine, 7-hydroxy-mitragynine, paynantheine, speciogynine, or speciociliatine postdose evaluable PK sample collected (based on viable PK samples).

Subjects who do not complete the blood sampling schedule may be included in the PK population for only the PK parameters that are judged not to be affected by the missing sample(s).

Subjects with protocol deviations or adverse events that could be considered to have an impact on the PK results may be excluded from the PK population. Participants who received only placebo will not be included in the PK population.

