**Table 9-3. Subjective Measures Schedule**

Category	Evaluations	Timepoints
Drug-specific VAS	Drug Liking, Good Drug Effects, Bad Drug Effects, and Any Drug Effects	0.25, 0.5, 1, 1.5, 2, 2.5, 3, 4, 6, 8, 10, 12, and 24 hours postdose
	Overall Drug Liking and Take Drug Again	12 and 24 hours postdose
Other VAS	High, Feeling Drunk, Relaxation/Agitation, Drowsiness/Alertness, and Bowdle VAS	Predose and 0.25, 0.5, 1, 1.5, 2, 2.5, 3, 4, 6, 8, 10, 12, and 24 hours postdose
	Drug Similarity	12 hour postdose
ARCI Scales	MBG, A, BG, PCAG, and LSD	Predose and 0.25, 0.5, 1, 1.5, 2, 2.5, 3, 4, 6, 8, 10, 12, and 24 hours postdose

Abbreviations: A = amphetamine; BG = Benzedrine Group; LSD = Lysergic Acid Diethylamide; MBG = Morphine-Benedrine Group; PCAG = Pentobarbital–Chlorpromazine–Alcohol Group; VAS = visual analog scale.

Windows for timed subjective measurements are presented in [Table 9-4](#).

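### Protocol 4.3.2 allows a dosed subject to be removed from the whole study for an event that only spoils the PK profile, which ends later safety and PD collection although SAP 4.3 already handles such events within the PK analysis

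*Protocol*

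**What the plan says.** Protocol 4.3.2, on the period after dosing, sets out who may act: "An Investigator may remove a subject from the study on the recommendation of the PK facility and/or Sponsor due to an unanticipated event". The Investigator decides, and the PK facility and Sponsor recommend. The qualifying events are described by their effect on the PK data, with examples: "could result in an inadequately characterized PK profile (e.g., a missed blood draw, an AE, meal deviation, concomitant medication intake, etc". No severity or timing threshold is attached to the AE example. The same section separately says that a subject may "be removed from the study at the discretion of an Investigator or Sponsor", and it has its own provision for withdrawal on safety grounds.

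For removed subjects, 4.3.2 says: "Attempts should be made to have such subjects complete the End-of-Study/Early Termination assessments". Protocol 3.1 is firmer and has early terminators perform the Follow-Up Visit procedures as soon as possible. Protocol 7.4 adds, with other endpoints besides resolution: "Any AE which remains unresolved as of the last visit will require an evaluation and follow-up until the AE has been resolved".

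SAP 4.3 deals with the same kinds of event inside the PK analysis. On missed samples it says: "Subjects who do not complete the blood sampling schedule may be included in the PK population for only the PK parameters"; the parameters meant are those which the gap leaves intact. Subjects whose deviations or AEs could affect the PK results may be left out of the PK population.

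Two key secondary PD scales, "Overall Drug Liking and Take Drug Again", are scheduled only at 12 and 24 h (SAP Table 9-3; Protocol Table 6-11).

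**The concern.** Safety and tolerability are the primary objective and PK is secondary (Protocol Table 2-1). Under this clause a problem with a secondary objective can stop collection of primary-endpoint data. In a single-dose study no further dosing is prevented, so the only effect is that the subject is no longer observed.

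An AE is an outcome and may become more frequent as dose rises. If AEs lead to removal, the assessments that go missing may be missing because of how the subject responded. With 6 active subjects per dose, one or two such removals matter. The Safety Review Committee reviews safety and PD data after each cohort (Protocol 3.1), so truncated records would reach escalation decisions as well as the final report.

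**Working it through.** The plan gives no removal rate, SD or sample-size calculation (Protocol 8.7), so there is no figure of its own to reproduce. The check has three steps.

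**1. What is kept.** The Safety population is every dosed subject, with no completion requirement (Protocol 8.1.2; SAP 4.2). Listings run up to discontinuation (SAP 5.1), and AEs leading to discontinuation are listed (SAP 10.1). The TEAE denominator stays at 6: if 2 of 6 have an event and one is removed, the rate is still 2/6 = 33.3%.

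**2. What is lost.** Scheduled postdose assessments through 48 h that fall after removal:

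| Series (Protocol table) | Scheduled | Lost after 2 h | After 4 h | After 12 h | After 24 h |
|---|---|---|---|---|---|
| Drug Liking (6-11) | 13 | 8 | 5 | 1 | 0 |
| Overall Drug Liking, Take Drug Again, each (6-11) | 2 | 2 | 2 | 1 | 0 |
| Blood pressure and pulse (6-3) | 6 | 4 | 3 | 2 | 1 |
| Respiratory rate (6-3) | 4 | 2 | 1 | 0 | 0 |
| ECG (6-5) | 4 | 3 | 2 | 2 | 1 |
| Spot SpO2 (6-4) | 9 | 7 | 5 | 0 | 0 |

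An end-of-study set, if obtained, returns one ECG, one set of laboratory tests, C-SSRS, physical examination, blood pressure and pulse (Tables 6-1 and 6-3). It contains no respiratory rate, SpO2 or PD measure. Missing safety values are in general not imputed (SAP 5.4).

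PD results are presented for the Completer population (SAP 9), which requires enough data for the primary endpoint, judged at blinded review, and a Drug Liking observation within 2 h of Tmax (SAP 4.4). An early removal may fail this test. TA_AOE is not calculated if the last scheduled point is missing (SAP 9).

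**3. What that could do, under stated assumptions.**

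*Precision.* Take one dose against pooled placebo, with 5 × 2 = 10 placebo subjects planned and a common SD. The SE in SD units is √(1/n + 1/10).
- n = 6: 0.516
- n = 5: 0.548 (+6.1%)
- n = 4: 0.592 (+14.6%)

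*Zero events on an assessment missing after removal.* The one-sided 95% upper bound is 1 − 0.05^(1/n): 39.3% for n = 6, 45.1% for n = 5 and 52.7% for n = 4. This does not apply to TEAE incidence.

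*Bias in a dose mean.* Assume normal scores, and that those removed are the lowest scorers and leave the PD analysis. The two lowest of six values average −1.266 and −0.641 SD (simulation, 1,000,000 replicates).
- Losing one raises the mean by 1.266/5 ≈ 0.25 SD.
- Losing two raises it by (1.266 + 0.641)/4 ≈ 0.48 SD.
- If removal is unrelated to score, the expected bias is 0.

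Direction is not fixed either. A removed subject who stays a Completer has Emax taken over fewer times, which can only equal or fall below the full-schedule value.

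**The case against.** The strongest reply is that the clause is narrow and its effects are limited. Much of this stands.

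- A reader might infer that removal erases safety data or hides the AE. It does not, as step 1 shows. The MTD definition and cohort stopping rules (Protocol 3.3 and 4.3.2.1.2) rest on AEs and SAEs, and the triggering AE still counts.
- A reader might infer that the PK facility or Sponsor can order removal under this sentence. They only recommend. The decision is the Investigator's, must be documented, and is discussed in the study report where appropriate. The Sponsor's wider discretion comes from a different sentence.
- The clause covers unanticipated events. Vomiting is the obvious AE that could spoil a PK profile, but the protocol foresees it: dosing takes place "following intake of a high-fat breakfast to avoid potential tolerability issues (i.e., vomiting"). It is therefore unclear whether vomiting falls within the clause. The ambiguity remains because unanticipated is not defined and an AE is listed without qualification.
- A reader might infer that those removed are the worst-tolerating subjects. That can fit only the AE trigger. A missed draw, meal deviation or concomitant medication need not reflect tolerability.
- Exclusion from the Completer population is not automatic. A subject removed after peak liking can keep a valid Drug Liking Emax.

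The reply does not explain why removal from the study is needed when exclusion from the PK analysis is available. That the power is discretionary does not help, because no criterion says when it should be used.

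**Conclusion.** The point holds as a design weakness that should be corrected. The clause can end scheduled safety and PD collection in a dosed subject for a reason that concerns PK alone, and SAP 4.3 makes this unnecessary. The certain part follows from the schedules: the counts in the table, and the loss of both 12 h and 24 h scales for anyone removed before 12 h.

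The bias is conditional. It requires an AE-triggered removal, a link between that AE and the scores, and either loss from the Completer population or loss of the late scales. The 0.25 and 0.48 SD shifts illustrate an extreme case under assumed normality and are not estimates. The documents support neither a claim that higher doses will look better tolerated on the primary AE data nor a claim that PD results will be biased. They support only the statement that such missingness is permitted and may be related to dose and tolerability.

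**What to change.** Amend the Protocol 4.3.2 sentence so that an event affecting only the PK profile leads to exclusion of the affected PK parameters, or of the subject from the PK population, under SAP 4.3. State that the subject continues all scheduled safety and PD assessments through the Follow-Up Visit.

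Leave the other withdrawal grounds as they are: withdrawal of consent, safety, behavior (4.3.2) and non-compliance (4.3.2.1.1). Add that a PK-only event is not by itself a reason for removal under the general discretion of the Investigator or Sponsor, or under non-compliance. Without this the same removal remains possible by another route.

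Inclusion in the PD analysis stays subject to the Completer criteria, and the Safety population definition needs no change.

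The cost is a change of wording in one protocol paragraph. No visits or procedures are added, because these subjects complete the schedule already planned.
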